Cover Page

Evaluation of the Effect of Intravitreal Injections of Anti-VEGF on Macular Perfusion in Diabetic Patients Using OCTA (IMPACT)

NCT03246152

Upload date: 12/25/2019

Review date: 4/3/2017

Faculty of Medicine, Cairo University Postgraduate Research Program Template

1. Proposed Study Title

Evaluation of the effect of repeated intravitreal injections of Anti-VEGF on macular perfusion in diabetic patients using optical coherence tomography angiography

2. Background and Rationale

Over the past few years, anti-vascular endothelial growth factor (VEGF) drugs have become the mainstay of therapy for diabetic macular edema (DME), substantially improving visual acuity for many diabetics worldwide, and proving effective for treatment of both non-proliferative and proliferative diabetic retinopathy.¹

The Early Treatment Diabetic Retinopathy Study (ETDRS) group founded guidelines for treating patients with clinically significant DME (CSME) with focal/grid macular laser photocoagulation.² Since then, macular laser, and steroids, were the main therapies for treatment of DME until anti VEGF drugs were developed after a growing body of scientific evidence implicated VEGF in the pathophysiologic process of DME.^{3,4}

Several explanations are present for how VEGF results in the dysfunction of the blood–retinal barrier in patients with DME, including (1) being an important mediator for several proinflammatory mediators in diabetic retinopathy (e.g. cytokines); (2) the direct effects on tight junction-associated proteins (as B-catenin and occludin); and (3) induction of pericyte degeneration and depletion.⁵

Many studies such as Diabetic Retinopathy Clinical Research [DRCR] Network studies, RESTORE Study,⁶ RISE and RIDE Research Group,⁷ and The BOLT Study⁸ have supported the use of anti-VEGF agents in the treatment of DME with better visual outcomes using anti-VEGF injections alone or in combination with other treatments.

One of these studies, The BOLT study, compared ETDRS macular laser treatment (MLT) to intravitreal bevacizumab in patients with persistent CSME. After 2 years, the bevacizumab group had a median of 9 letters gained, compared to 2.5 letters for the MLT group ($p = 0.005$).⁸

Several ocular complications of intravitreal anti-VEGF injections have been reported including endophthalmitis, cataract and retinal detachment. The effect of anti-VEGF drugs on macular perfusion has been inconclusive, with mixed reports of increase, decrease or no effect on perfusion in response to anti-VEGF treatment. In

many of these studies, however, patients with more ischaemic retinas were not included.^{8,9} Retinal ischemia is an important factor in the progression and prognosis of diabetic retinopathy.

Some studies showed sustained retinal arteriolar vasoconstriction in eyes treated with anti-VEGF,¹⁰ while others demonstrated using ultrasound decreased blood flow velocities in all retrobulbar arteries after intravitreal anti-VEGF injections.¹¹ This could indicate that anti-VEGF agents may have an effect on the ocular perfusion.

Fluorescein angiography (FA) was the method used to assess changes in macular perfusion after anti-VEGF injections in most of the studies.^{6,7,8} Despite its clinical usefulness, however, FA is known to have documented risks.¹² Optical coherence tomography angiography (OCTA) is a new noninvasive method of acquiring high-resolution images of the retinal vasculature that can be utilized in the treatment of retinal disease without the need for dye injection. It allows the visualization of both the superficial and deep retinal capillary layers separately and the construction of microvascular flow maps.¹³

OCTA uses high-speed OCT scanning to detect the flow of blood by analyzing signal decorrelation between two sequential OCT cross-sectional scans repeated at the same location. Because of the movement of erythrocytes within a vessel, compared to stationary areas of the surrounding retina, only perfused blood vessels will result in signal decorrelation, leading to their imaging. The split-spectrum amplitude decorrelation angiography (SSADA) algorithm improves the signal to noise ratio.¹⁴

Several studies have proved the reliability of OCTA in detecting and quantifying macular ischemia in diabetics.^{14,15,16}

In our study, we aim to evaluate the effect of repeated intravitreal injections of Anti-VEGF on the perfusion of different capillary layers in the macula of diabetic patients using OCTA.

3. Objectives

To study the effect of repeated intravitreal injections of Anti-VEGF on macular perfusion in diabetic patients using optical coherence tomography angiography

4. Study Design

Prospective interventional study

5. **Ethical committee approval:** Yes

6. **Study Methods**

Type 1 and 2 diabetic patients requiring intravitreal Anti-VEGF injections for treatment of center involving diabetic macular edema

Inclusion criteria:

1) Patients \geq 18 years old with type 1 or 2 diabetes mellitus with decreased BCVA due to diabetic macular edema and center involvement by the edema on spectral domain optical coherence tomography (SD OCT) with any stage of diabetic retinopathy

Exclusion criteria:

- 1) Ocular conditions that may affect macular perfusion (e.g. retinal vascular diseases, uveitis, vasculitis etc.)
- 2) History of vitreoretinal surgeries (excluding intravitreal injections)
- 3) Any previous treatment for diabetic macular edema
- 4) Presence of epiretinal membrane involving the macula or vitreomacular traction
- 5) Media opacity preventing good image quality
- 6) Uncontrolled glaucoma
- 7) Thromboembolic events within 6 months

Methodology in details

This is a prospective interventional study to evaluate the effect of repeated intravitreal injections of Anti-VEGF on macular perfusion in diabetic patients using optical coherence tomography angiography (OCTA).

Each patient will receive a detailed ophthalmologic examination including measurement of BCVA as well as applanation tonometry, undilated and dilated slit-lamp biomicroscopic examination and indirect fundus examination.

Duration of diabetes and its control through HbA1C measurement will be recorded for each patient.

Type 1 and 2 diabetic patients found to have BCVA worse than 6/6 and

clinical evidence of macular edema will undergo SD OCT and FA.

Patients with center involved macula edema detected by SD OCT will be included in the study and will undergo baseline macular OCTA.

These patients will then undergo intravitreal injections of Anti-VEGF monthly for 3 months then OCTA will be repeated to evaluate changes in macular perfusion and SD OCT will be repeated to assess retinal thickness. Patients with center involving macular edema on SD-OCT after the first 3 injections will continue to receive intravitreal Anti-VEGF injections monthly until the edema subsides or the study duration ends. These patients then undergo a final macular OCTA for perfusion evaluation and SD OCT for thickness assessment.

OCTA will be performed with an Avanti RTVue XR system (Optovue, Inc., Fremont, CA, USA). Area of FAZ and capillary density at each capillary layer will be calculated before and after interventions using the OCTA machine software and ImageJ software.

All statistical analyses will be done using IBM SPSS v20.0 statistical software (IBM Corporation, NY, USA). Descriptive statistics will be calculated, and the data will be summarized as mean \pm SD for numerical data, and as frequencies and percentages for categorical data.

Possible Risk (mention if there is any risk or not)

Risk of cataract, glaucoma, endophthalmitis, retinal detachment, central retinal artery occlusion and vitreous hemorrhage

Primary outcomes

1- Effect of repeated intravitreal Anti-VEGF injections on Foveal Avascular Zone (FAZ) area and capillary density as a measure of macular perfusion change at different capillary levels in the macula.

Secondary outcome parameters

1- Effect of intravitreal Anti-VEGF injections on microaneurysms and vascular changes in the superficial and deep capillary plexuses of the macula using OCTA

2- Effect of intravitreal Anti-VEGF injections on choriocapillaris density using OCTA

3- Correlation of BCVA with degree of capillary non-perfusion before and after injections

Sample size (number of participants included)

50 eyes

Source of funding (is there any source of funds or not)

Self

7. Time plan

6 months from first injection

References:

1. Radwan S. Ajlan, Paolo S. Silva & Jennifer K. Sun (2016) Vascular Endothelial Growth Factor and Diabetic Retinal Disease, *Seminars in Ophthalmology*, 31:1-2, 40-48, DOI: 10.3109/08820538.2015.1114833
2. Early Treatment Diabetic Retinopathy Study Research Group. Photocoagulation for diabetic macular edema: Early Treatment Diabetic Retinopathy Study report number 1. *Arch Ophthalmol* 1985; 103:1796–806.
3. Regression of retinal and iris neovascularization after intravitreal bevacizumab (Avastin) treatment. *Retina* 2006; 26:352– 4.
4. Pegaptanib: a novel approach to ocular neovascularization. *Ann Pharmacother* 2006;40:1322– 6.

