**Cover Page**  
**Evaluation of the Effect of Intravitreal Injections**  
**of Anti-VEGF on Macular Perfusion in Diabetic**  
**Patients Using OCTA (IMPACT)**  
**NCT03246152**

**Document date: 5/16/2019**

**Upload date: 1/13/2020**

**Statistical methods:**

Data were coded and entered using the statistical package SPSS (Statistical Package for the Social Sciences) version 25. Data was summarized using mean, standard deviation, median, minimum and maximum in quantitative data and using frequency (count) and relative frequency (percentage) for categorical data. Comparisons between quantitative variables were done using the non-parametric Kruskal-Wallis and Mann-Whitney tests. For comparison of serial measurements within same patients paired t test was used in normally distributed quantitative variables while non-parametric Wilcoxon signed rank test was used for non-normally distributed quantitative variables (*Chan, 2003a*). Correlations between quantitative variables were done using Pearson or Spearman correlation coefficient (*Chan, 2003b*). Linear regression

analysis was done to predict changes in different parameters using baseline data (*Chan, 2004*). P-values less than 0.05 were considered as statistically significant.

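### No masking to visit and no reading order are specified for the OCTA measurements behind an uncontrolled before/after primary result

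*Protocol*

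**What the plan says.** The primary outcome is the effect of repeated injections on "Foveal Avascular Zone (FAZ) area and capillary density as a measure of macular perfusion change at different capillary levels in the macula" (Protocol, section 6, Primary outcomes). The only account of how it is measured is in the OCTA paragraph of section 6: the values "will be calculated before and after interventions using the OCTA machine software and ImageJ software". That paragraph names the scanner. It does not say who reads the images, how many readers there are, which program gives which parameter, or which steps are automated.

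Section 4 of the protocol describes the design only as "Prospective interventional study", with no control group. Under Methodology in details, all included patients have a baseline scan and then follow one path: "These patients will then undergo intravitreal injections of Anti-VEGF monthly for 3 months then OCTA will be repeated to evaluate changes in macular perfusion". Those whose edema persists continue treatment and have a final scan later.

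The SAP (Statistical methods) tests change within patients: "For comparison of serial measurements within same patients paired t test was used in normally distributed quantitative variables", with the Wilcoxon signed rank test as the alternative for non-normal data. It also names Kruskal-Wallis and Mann-Whitney tests but defines no groups for them, so they supply no concurrent control. Neither document mentions masking, image coding, reading order, duplicate reading or reader agreement.

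**The concern.** Because everyone is treated between scans, visit order and treatment status are the same thing. In a controlled trial, a reader's tendency to draw borders or set thresholds differently at follow-up would affect both arms, and much of it would cancel in the comparison. Here nothing cancels it. A consistent shift between baseline and follow-up readings adds directly to the mean change and would be reported as a change in perfusion.

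The exposure lies in the operator-dependent steps. Examples are tracing the FAZ or choosing a threshold in ImageJ, or correcting the machine software's output by hand. The protocol does not say which of these occur, so the risk can be neither sized nor dismissed from the documents. The protocol's Background section describes the prior evidence on perfusion as mixed, which makes a measurement protected from expectation more valuable.

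**Working it through.** **Reproducing the plan's figure.** The plan states 50 eyes. It gives no power, effect size, SD of change or dropout rate, so that number cannot be reproduced. The point does not depend on it.

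**Inputs**
- n = 50 pairs, from 50 eyes (Protocol, Sample size). Independence is assumed; the protocol does not say one eye per patient.
- Test: paired t (SAP, Statistical methods).
- Alpha = 0.05: "P-values less than 0.05 were considered as statistically significant". The SAP does not state sidedness; two-sided is assumed.
- True change: zero.
- b = systematic reading shift between visits, in units of the SD of the paired change. This is assumed and varied from 0 to 0.3, because the documents give no reader-agreement figure.

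**Formula.** With a shift b, the paired t statistic follows a noncentral t distribution with 49 degrees of freedom and noncentrality b × √50 = 7.071 × b. The two-sided critical value is 2.01. The false-positive rate is P(T > 2.01) + P(T < −2.01). As a check, the normal approximation is Φ(b√50 − 1.96) + Φ(−b√50 − 1.96).

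| Assumed shift b (SD) | Noncentrality | False-positive rate | Normal check |
|---|---|---|---|
| 0 | 0 | 0.050 | 0.050 |
| 0.05 | 0.354 | 0.064 | 0.064 |
| 0.1 | 0.707 | 0.107 | 0.109 |
| 0.2 | 1.414 | 0.284 | 0.293 |
| 0.3 | 2.121 | 0.548 | 0.564 |

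**For scale.** An observed mean change of 2.01/√50 = 0.284 SD is enough for p < 0.05. A true change of about 0.40 SD is needed for 80% power. A shift of 0.2 SD is therefore half of the change that the study could detect with 80% power.

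These rates are for one paired comparison. They show how sensitive the test is to a hypothetical shift; they do not estimate the shift in this trial.

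**Number of image sets to code.** With two OCTA visits, 50 × 2 = 100. If every eye had a third, 50 × 3 = 150.

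**The case against.** The strongest reply has four parts.

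- **Silence is not evidence of unmasked reading.** This stands. A reader might infer that the images were, or will be, read with the visit known. The documents do not show that; they do not describe the reading procedure at all. The supportable statement is that no masking is specified.
- **The measurement may be automated.** This partly stands. A value taken straight from the machine software leaves little room for expectation, and the shift would then be close to zero. But the protocol adds ImageJ without saying what it is used for, so automation cannot be presumed either.
- **No direction of bias is shown.** This also stands in part. Inflation requires a consistent one-way shift. The Background section reports increases, decreases and no effect, though it also cites arteriolar narrowing and lower flow velocities after anti-VEGF treatment. Some expectation is plausible, but the documents establish no dominant one.
- **Edema reveals the visit anyway.** This limits the benefit of masking. Inclusion requires center-involving edema and treatment aims to clear it, so where edema can be seen on the images being read, many responding eyes may be identifiable as baseline or follow-up. Eyes with persistent edema, which the protocol provides for, would be better protected; their share is unknown. Coding still removes dates and stops one visit being read against the other's value.

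**Conclusion.** The gap is real and worth closing. No masking or reading order is specified for a primary outcome that rests wholly on a before/after difference without a control arm. Any systematic shift from an operator-dependent step would enter that difference in full.

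The size is conditional. The illustrative false-positive rates run from 5% with no shift to 55% with a shift of 0.3 SD. They rest on assumed shifts, on independent eyes and on a two-sided paired t test. Fully automated output belongs near 5% to 6%; heavy manual input could place it higher.

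A reader might go further and conclude that both primary parameters are biased, or that the upper rates describe this trial. The documents support neither conclusion, because they do not say which steps are manual and give no figure for reader variation.

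**What to change.** Amend the OCTA paragraph in section 6 of the protocol as follows.

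1. For each parameter, name one tool and one group of fixed settings to be used at all visits, and state which steps are automated and which depend on an operator.
2. For every operator-dependent step, remove date and visit from the images, give them random codes, and have the study's own reader measure them in random order. Lock the readings before the code is broken.
3. Where the machine software cannot work on coded files, use its automated output without manual correction, or have any correction made without sight of the other visit's values.

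If every step proves to be automated, one sentence saying so largely settles the point.

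**Cost.** The work is coding and shuffling about 100 to 150 image sets. No extra patient, scan or reader is needed, and the sample size does not change. Readings have to wait until follow-up ends, which the Time plan puts at 6 months from first injection.

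**Limits.** Masking will be partial, because edema resolution may reveal the visit. It does not correct segmentation artefact, which can change as edema resolves, and it does not replace a control group.

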**Cover Page**  
**Evaluation of the Effect of Intravitreal Injections**  
**of Anti-VEGF on Macular Perfusion in Diabetic**  
**Patients Using OCTA (IMPACT)**  
**NCT03246152**

**Document date: 5/16/2019**

**Upload date: 1/13/2020**

**Statistical methods:**

Data were coded and entered using the statistical package SPSS (Statistical Package for the Social Sciences) version 25. Data was summarized using mean, standard deviation, median, minimum and maximum in quantitative data and using frequency (count) and relative frequency (percentage) for categorical data. Comparisons between quantitative variables were done using the non-parametric Kruskal-Wallis and Mann-Whitney tests. For comparison of serial measurements within same patients paired t test was used in normally distributed quantitative variables while non-parametric Wilcoxon signed rank test was used for non-normally distributed quantitative variables (*Chan, 2003a*). Correlations between quantitative variables were done using Pearson or Spearman correlation coefficient (*Chan, 2003b*). Linear regression

analysis was done to predict changes in different parameters using baseline data (*Chan, 2004*). P-values less than 0.05 were considered as statistically significant.

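### The sample is counted in eyes with no one-eye rule, and no planned test allows for two eyes of one patient, so the before-after tests may reject too often

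*SAP*

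**What the plan says.** Protocol section 6 gives the sample as 50 eyes, under a heading that asks for participants: "Sample size (number of participants included". No number of patients appears in either document.

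Eligibility is written by patient (section 6, Methodology in details): "Patients with center involved macula edema detected by SD OCT will be included in the study and will undergo baseline macular OCTA". There is no limit to one eye and no rule for choosing a study eye. One exclusion criterion is "Any previous treatment for diabetic macular edema", with no indication of whether it applies to the patient or to the eye.

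The primary outcome is "Effect of repeated intravitreal Anti-VEGF injections on Foveal Avascular Zone (FAZ) area and capillary density as a measure of macular perfusion change". Both quantities are measured in an eye.

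The SAP (Statistical methods) states: "For comparison of serial measurements within same patients paired t test was used in normally distributed quantitative variables". The Wilcoxon signed rank test is used when data are not normally distributed. It also lists Kruskal-Wallis and Mann-Whitney tests, Pearson or Spearman correlation, and a linear regression whose purpose is given as "analysis was done to predict changes in different parameters using baseline data". The significance rule is "P-values less than 0.05 were considered as statistically significant". It names no averaging per patient, eye selection, mixed model, GEE or clustered standard error.

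**The concern.** Every test the SAP lists treats its units as independent. If the unit is the eye and some patients supply two, that assumption can fail, because fellow eyes share the patient's systemic disease and may respond alike.

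The paired tests do not cure this. Pairing removes the correlation between the earlier and later readings of the same eye. What remains is the correlation between the change in the right eye and the change in the left. When it is positive, 50 changes carry less information than 50 independent ones, the standard error is too small, and the p-value is too low.

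The before-after tests are the ones that bear on the primary outcomes, and the protocol describes no comparator arm. Without the number of patients, a reader cannot tell whether a p-value near 0.05 is affected, or by how much.

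A regression of change on a factor shared by both eyes has the same problem. The SAP names no predictors, but the protocol does collect such factors: "Duration of diabetes and its control through HbA1C measurement will be recorded for each patient".

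**Working it through.** **Inputs from the documents.** 50 eyes (Protocol section 6); significance level 0.05 (SAP), taken as two-sided because sidedness is not stated; paired t or Wilcoxon test on the changes (SAP). The figure of 50 cannot be reproduced, because no effect size, standard deviation, power or dropout rate is given.

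**Assumed inputs.** B, the number of patients with both eyes in the study, and r, the correlation between the changes (not the levels) of fellow eyes. The documents give neither, so both are varied. The number of patients is P = 50 − B.

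**Formulas.**

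- Design effect: DE = 1 + r × 2B/50
- Actual two-sided error of the unadjusted test: 2 × [1 − Φ(1.96/√DE)]
- Effective number of eyes: 50/DE

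**Worked case, B = 10, r = 0.5.** DE = 1 + 0.5 × 20/50 = 1.20. Then 1.96/√1.20 = 1.79, so the actual error is 7.4%. The effective number of eyes is 50/1.20 = 41.7.

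**Actual error at nominal 5%:**

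| Bilateral patients B (patients P) | r = 0 | 0.1 | 0.3 | 0.5 | 0.7 |
|---|---|---|---|---|---|
| 0 (50) | 5.0% | 5.0% | 5.0% | 5.0% | 5.0% |
| 5 (45) | 5.0% | 5.2% | 5.7% | 6.2% | 6.6% |
| 10 (40) | 5.0% | 5.5% | 6.4% | 7.4% | 8.3% |
| 25 (25) | 5.0% | 6.2% | 8.6% | 11.0% | 13.3% |

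**Simulation check.** 50 eyes, normally distributed changes, no true change, 40,000 runs per setting, with eyes as units:

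| Test | B | r = 0 | 0.1 | 0.3 | 0.5 | 0.7 |
|---|---|---|---|---|---|---|
| Paired t | 10 | 4.9% | 5.5% | 6.5% | 7.6% | 8.2% |
| Paired t | 25 | 5.0% | 6.1% | 8.5% | 11.1% | 13.5% |
| Wilcoxon | 10 | 4.7% | 5.4% | 6.3% | 7.3% | 7.9% |
| Wilcoxon | 25 | 4.9% | 6.0% | 8.3% | 10.9% | 13.1% |
| Regression, patient-level predictor | 10 | 4.9% | 5.5% | 6.5% | 7.4% | 8.3% |
| Regression, patient-level predictor | 25 | 5.1% | 6.3% | 8.8% | 11.1% | 13.8% |

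The simulated rates agree with the formula. After the two eyes of each bilateral patient are averaged, the rates over the same settings are 4.8–5.2% for the paired t test, 4.8–5.2% for Wilcoxon and 4.9–5.1% for the regression.

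The between-group tests are not quantified, because the SAP defines no groups.

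**The case against.** The strongest reply is that nothing shows any patient gave two eyes. The sample-size heading asks for participants, the procedures are described patient by patient, and the SAP speaks of repeated measurements in the same patients. Fifty patients with one study eye each is a natural reading. The prior-treatment exclusion, read per patient, would also bar a fellow eye that presents after the first has been treated.

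This has weight, and the point is conditional for that reason. But neither document states the one-eye reading. Even the strict reading of the exclusion leaves room for two untreated eyes entered together.

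A second reply is that the harm needs several things at once: bilateral patients, eyes analysed as separate units, and positively correlated changes. That is correct. With 5 bilateral patients the error is at most 6.6% over the range shown. The rates of 11% and above need all patients bilateral and a correlation of at least 0.5. A negative correlation would make the tests conservative (4.1% at B = 10, r = −0.2).

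Third, the regression point is limited to predictors shared by both eyes. A predictor that is independent between fellow eyes gave 4.7–5.3% in simulation, so no inflation. Baseline FAZ area or capillary density, measured per eye, would fall between the two cases. That limit stands.

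**Conclusion.** The concern holds in conditional form. The plan as written admits both eyes of a patient and has no method to handle them. If that happened, the primary before-after tests are anti-conservative whenever fellow-eye changes correlate positively. The effect is trivial at low correlation or with few bilateral patients, and material only when both are substantial. There is none with one eye per patient.

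The sizes rest on assumed values of B and r, a two-sided test, and, in the simulations, normally distributed changes. Confidence is medium, because the documents do not show whether any patient was bilateral. It should be fixed: the possible error touches the primary inference, and the correction is cheap.

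**What to change.** 1. Report the numbers of patients, eyes and bilateral patients. If no patient is bilateral, say so and keep the planned tests; the cost is that one sentence.
2. If any patient is bilateral, average the two eyes' changes and apply the SAP's own paired t or Wilcoxon test to the patient means. Each patient then counts equally, and this change of weighting should be stated.
3. Alternatively, keep eyes as units and cluster on patient: robust standard errors or GEE with a small-sample correction, or change scores with a random patient intercept.
4. Treat the regressions the same way. Where a predictor is measured per eye, clustering keeps within-patient information that averaging discards. The same principle applies to the correlations and the rank comparisons.

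This is re-analysis of existing data, with some loss of precision. Relative to the unclustered standard error, clustering adds √DE − 1. Averaging adds √(50 × [(50 − 2B) + B(1 + r)/2]/P²) − 1. For B = 10 and r = 0.5 the latter is √(50 × [30 + 7.5]/1600) − 1 = 8%.

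| Increase in standard error | r = 0 | 0.1 | 0.3 | 0.5 | 0.7 |
|---|---|---|---|---|---|
| B = 10, clustering | 0% | 2% | 6% | 10% | 13% |
| B = 10, averaging | 5% | 5% | 7% | 8% | 10% |
| B = 25, either | 0% | 5% | 14% | 22% | 30% |

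With averaging, the paired t test's degrees of freedom fall from 49 to 39 (B = 10) or 24 (B = 25).

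### The protocol names no hypothesis test or alpha; the tests and the unadjusted 0.05 rule first appear in a later SAP written in the past tense, so they are not shown to be pre-specified and cover several primary comparisons.

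*SAP*

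**What the plan says.** **Protocol.** The cover page carries "Review date: 4/3/2017". The statistics paragraph in section 6 (Study Methods) has two sentences. The first is about software: "All statistical analyses will be done using IBM SPSS v20.0 statistical software". The second begins "Descriptive statistics will be calculated, and the data will be summarized as mean" and goes on to SD, frequencies and percentages. It gives no test, model or significance level.

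Other parts of section 6 go further than summaries. FAZ area and capillary density are to be calculated for each capillary layer before and after treatment. Methodology in details sets OCTA at baseline and after three monthly injections, with a final OCTA for patients who go on being injected. The primary outcome is the effect of injections on FAZ area and capillary density at the different capillary levels. Secondary outcome 3 is a correlation of BCVA with capillary non-perfusion, with no coefficient or test named.

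**SAP.** The cover page carries "Document date: 5/16/2019". Statistical methods opens with "Data were coded and entered using the statistical package SPSS" (version 25) and stays in the past tense. It lists Kruskal-Wallis and Mann-Whitney tests, Pearson or Spearman correlation, and linear regression on baseline data. For change over time it says "For comparison of serial measurements within same patients paired t test was used in normally distributed quantitative variables", with Wilcoxon signed rank as the alternative when data are not normal. P below 0.05 is the significance rule for all of them. The SAP names no primary test, multiplicity rule or normality criterion, and does not define the groups to be compared.

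**The concern.** A p-value below 0.05 carries a 5% error rate only for a comparison and test fixed before the data were seen, and only for that one comparison. Two things weaken this here. The documents do not show that the tests were fixed in advance. And even if they were, one unadjusted threshold is applied to a primary outcome made up of several comparisons.

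At stake is how the main result is read. A significant change in FAZ area or density at one layer and one visit could be taken as a confirmed perfusion effect, when the plan supports only an exploratory reading.

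**Working it through.** **1. What each document fixes**

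| Item | Protocol (review date 4/3/2017) | SAP (5/16/2019) |
|---|---|---|
| Before/after measurement of FAZ area and density per layer | Yes | Serial within-patient comparison, variables not named |
| Correlation | BCVA with non-perfusion, no method | Pearson or Spearman, no rule for choosing |
| Within-patient test | None | Paired t or Wilcoxon, by normality |
| Between-group tests | None | Kruskal-Wallis, Mann-Whitney, groups undefined |
| Regression | None | Linear, outcomes and predictors not named |
| Alpha | None | 0.05 for every p-value |
| Single primary variable | None | None |

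Neither document gives a last-visit, data-lock or first-analysis date. The tests are therefore not shown to be pre-specified, and the order of test choice and data access cannot be settled from the text.

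**2. The plan's only error-rate figure**

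For one fixed test, 1 − (1 − 0.05)^1 = 0.05. The SAP's threshold is reproduced for a single comparison.

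**3. Size of the primary family**

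The documents give no count. Assume 2 measures (FAZ area, capillary density) x 2 layers (superficial, deep) x 2 post-baseline time points = 8. The second time point is planned for the patients who continue injections, so 8 is a working figure. The results for 4 and 12 comparisons show the range: 4 is one time point only, and 12 is all three pairwise visit comparisons (2 x 2 x 3).

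**4. Chance of at least one false positive**

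With m independent two-sided tests and no true change, the rate is 1 − 0.95^m:
- m = 4: 1 − 0.8145 = 18.5%
- m = 8: 1 − 0.6634 = 33.7%
- m = 12: 1 − 0.5404 = 46.0%

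With equal correlation ρ between test statistics, take Z_i = √ρ·U + √(1 − ρ)·e_i, where U and e_i are standard normal. Count the share of 200,000 draws in which any |Z_i| exceeds 1.96:

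| Comparisons | ρ = 0.3 | ρ = 0.5 | ρ = 0.8 |
|---|---|---|---|
| 4 | 17.3% | 15.6% | 11.6% |
| 8 | 30.0% | 25.0% | 15.7% |
| 12 | 39.5% | 31.8% | 18.6% |

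**5. Does choosing between t and Wilcoxon matter?**

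This was simulated with 50 independent paired differences (the protocol's 50 eyes), no true mean change and 20,000 runs. The SAP gives no normality criterion, so a Shapiro-Wilk test at 0.05 was assumed:
- Normal differences: 5.2% rejections.
- t with 3 df (symmetric, heavy tails): 5.0%.
- Exponential differences centred at mean zero (strongly skewed): 22%. Wilcoxon then tests a different null from zero mean change, so this does not measure a lack of pre-specification.

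For symmetric data the normality-based choice adds almost nothing. The excess over 5% comes from the number of comparisons.

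**The case against.** The strongest reply is that the main analysis was foreseen. The protocol plans the before/after calculation of the primary variables, fixes the scan occasions and lists the BCVA correlation. Only the test and alpha are missing, and a paired t or Wilcoxon test is the obvious choice for such data. This stands. A reader might infer from the statistics paragraph that the protocol intended description only, but its outcome and methods text does not support that.

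A reader might also infer from the past tense and the mention of data entry that the tests were picked after results were known. The documents do not support that either. Tense shows when the text was written, and entering data is not the same as having seen results.

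A third reply is that the inflated error rates would be the same had every test been listed in 2017. That is correct: they measure multiplicity and cannot be used as the size of a timing problem. The SAP also nowhere calls its tests pre-specified or confirmatory. It does, however, apply a significance rule to all of them without qualification or adjustment. The change from SPSS v20.0 to version 25 is housekeeping, with no effect on these analyses shown.

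**Conclusion.** The point holds in two separate parts. First, no test or alpha is in the protocol, and all of them first appear in the SAP about two years after the protocol's review date, so they are not shown to be pre-specified. This part has no numerical size, and it is not a finding that the tests were chosen after the results. Second, the unadjusted 0.05 rule over a primary outcome with several components gives a family-wise false-positive rate above 5%. It is about 16% (correlation 0.8) to 34% (independent) for 8 comparisons. The second part rests on the assumed count, equal correlation between tests and two-sided testing; the SAP does not state sidedness. With 4 to 12 comparisons and correlation 0.3 to 0.8, the range is about 12% to 40%.

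**What to change.** In the SAP, state when the tests were chosen relative to data access, and cite any dated earlier plan.

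Unless such a plan is cited:
- Report the mean paired change with 95% confidence interval for FAZ area and for capillary density, per layer, as the main result.
- Replace the blanket significance rule with this label for p-values: exploratory, test not specified in the protocol, unadjusted for multiplicity.

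The sponsor should not be asked to declare that the tests were added after data entry, since the documents do not establish it. Nor should all p-values be labelled post hoc, since the before/after comparison and the BCVA correlation were foreseen in the protocol. An earlier plan would settle the timing, but the p-values would still be unadjusted unless that plan named a primary variable or an adjustment. The SPSS version can be aligned in the same edit.

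The cost is wording in the SAP and report, plus intervals computed from data that the SAP describes as already entered. The downside is that the results are presented as less confirmatory.
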